7.5.3 Additional variables

7.5.3.1 Health care and home care resource use

The subjects will be given a home diary for recording their use of health and home care resources. The diary will be filled in on a weekly basis. Any hospital inpatient days, other institutional care, any additional hospital emergency unit visits, days in other institutional care, and any outpatient visits to physicians or other relevant service providers will be recorded. In addition, all non-medical assistive devices that the subjects have in use at baseline are recorded, and thereafter all new devices that they start using due to ALS will be recorded in the diary each week. Regarding home care, the diary will contain information of the number of formal (paid/public services) and informal (unpaid e.g. by spouse, other family members, friends or other volunteers) home care hours received. Additionally, information will be collected about the number of times such home care has been received during the nighttime. Details of the home diary will be described in a separate document.

Health and home care resource use data will be aggregated over the course of the study for each subject, and summarised using descriptive statistics. Any further analysis for potential pharmacoeconomic purposes will be reported separately.

Time to any assistive device and any respiratory assistive device will be analysed as additional endpoints. They are analysed following the strategy outlined for other time-to-event endpoints in section [7.5.2.3](#).

7.5.4 Sensitivity analyses

All sensitivity analyses are performed based on the ITT population, unless otherwise specified.

7.5.4.1 Full analysis set

Method:

- Use the FAS population (see [6.1](#)).

Analyses that will be adjusted:

- Primary analysis SVC MMRM
- CAFS through 48 weeks
- Time to respiratory event
- CGI through 48 weeks
- Supine Borg CR 10 scale at 12 weeks
- Slope of change in the ALSFRS-R respiratory domain through 48 weeks

7.5.4.2 Per-protocol population

Method:

- Use the appropriate PP population (see [6.1](#)).

Analyses that will be adjusted:

- With PP up to week 12 (PP1):
 - Primary analysis SVC MMRM
 - Supine Borg CR 10 scale at 12 weeks
- With PP up to week 48 (PP2):
 - CAFS through 48 weeks
 - Time to respiratory event
 - CGI through 48 weeks
 - Slope of change in the ALSFRS-R respiratory domain through 48 weeks

7.5.4.3 Use randomisation strata from CRF data

Method:

- Adjust for STRATAV instead of STRATAR in models. This corrects for randomisations stratified based on incorrect information about stratification factors.

Analyses that will be adjusted:

- Primary analysis SVC MMRM
- Slope of change in the ALSFRS-R respiratory domain through 48 weeks

7.5.4.4 Analyses without missing data imputation

Method:

- Do not use missing data imputation; drop observations that list an imputation method.

Analyses that will be adjusted:

- All efficacy analyses performed with missing data imputation. See [6.2.5](#).

7.5.4.5 Include unacceptable quality SVC measurements

Method:

- Do not treat SVC measurements with unacceptable quality as missing.

Analyses that will be adjusted:

- Primary analysis SVC MMRM.
- All analyses of time-to-event endpoints with SVC components.

7.5.4.6 Exclude subjects that changed SVC supine angle during the study

Method:

- Use a new analysis population consisting only of subjects who had the same SVC supine measurement angle throughout their study visits.

Analyses that will be adjusted:

- Primary analysis SVC MMRM.
- All analyses of time-to-event endpoints with SVC components.

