6.2 Efficacy assessments

6.2.1 Slow Vital Capacity

The primary efficacy variable will be the change from baseline at 12 weeks in SVC measured in the supine position, SVC (supine). All SVC measurements prior to 12 weeks will be included in the statistical model. SVC is the maximum volume of air that can be exhaled slowly after slow maximum inhalation. The best read from 3 attempts will be chosen. The volume is measured in litres and the SVC variable will be % of predicted (normal) value for age, height and sex. In

DNO 090017ff823c9bac / 1.0 Approved 32 / 58

addition, time to decline in supine from baseline SVC by \geq 20% and time to supine SVC \leq 50% of predicted will be assessed.

SVC (supine) will be assessed once at each visit during the study including the baseline (visit 1), i.e. in the morning before the study treatment administration.

SVC will be assessed in the sitting and supine position at screening visit. Sitting SVC will be one of the inclusion criteria. Supine SVC is assessed at screening and baseline to ensure that the subject is able to perform it successfully when entering the study.

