2. OVERALL STUDY DESIGN AND PLAN

This is a randomised, double-blind, placebo-controlled, parallel-group, multinational, multicentre phase III study. The subjects will be allocated to 2 parallel groups receiving either levosimendan 1-2 mg daily or placebo in 2:1 ratio. The study will be conducted globally. The estimated number of sites is approximately 100.

The total duration for double-blind comparison will be 48 weeks. The primary efficacy analysis will be based on data collected from the first 12 weeks of the study. Two futility/interim analyses will be conducted: the first when approximately 50%, and the second when all of the subjects have been treated for 12 weeks. An independent data and safety monitoring board (DSMB) will be established for this and for safety monitoring purposes.

There will be a screening visit, a baseline visit (V1) followed by visits at 2 weeks (V2), 4 weeks (V3), 8 weeks (V4), 12 weeks (V5), 24 weeks (V6), 36 weeks (V7) and 48 weeks (V8), and telephone contacts during weeks 18, 30 and 42. An end-of-study visit will take place 14-25 days after the last study treatment administration for each subject. Additional visits may take place after visit 3 and after later visits. The total study duration for each subject will be about 51-52 weeks, including the end-of-study visit. The study design is presented in [Figure 1](#).

¹ Dose will be increased if the 1 mg/day dosing was well tolerated

² Dose can be decreased back to 1 mg/day if required for any reason. In case the dose was decreased due to HR increase > 30 bpm, additional visit will take place after approx. 2 weeks

³ Any time during the week

Figure 1. Study design

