6. GENERAL STATISTICAL CONSIDERATIONS

6.1 Data sets to be analysed

The intent-to-treat (ITT) population, including all randomized subjects, will be used for the primary evaluation. All subjects who received any study treatment will be included in the evaluation of safety. Sensitivity analyses will include evaluations of key endpoints in the full analysis set (FAS), including all treated subjects with at least a baseline and one post-baseline SVC measurement, and in the per-protocol (PP) population.

The PP population includes all randomized subjects, excluding subjects with important protocol deviations affecting the evaluation of efficacy. The study has two key intervals at which efficacy endpoints are generally evaluated: up to week 12, and up to week 48. For endpoints evaluated at week 12, it would not be desirable to exclude subjects from the PP analyses due to important protocol deviations occurring only after the endpoint has already been assessed. To address this, two separate PP populations will be created: PP up to week 12 (PP1) and PP up to week 48 (PP2). Important protocol deviations occurring before week 12 will lead to exclusion from both populations, while deviations occurring only after the week 12 visit has already been completed will only exclude the subject from PP2. The appropriate PP population will then be chosen for the analyses, according to the endpoint.

The importance of protocol deviations with respect to leading to exclusion from the PP populations will be evaluated during subject classification review meetings with the clinical study team. General principles that lead to exclusion contain: inclusion and exclusion criteria deviations, completeness of key efficacy assessments, use of prohibited medications, compliance and other important protocol deviations; and are detailed in a separate subject classification document.

Subject classification will be completed during the blind review before the database lock and opening of the treatment code.

Analyses of the effects of the COVID-19 pandemic are detailed in section [7.10.3](#).

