Primary efficacy will be evaluated based on the fitted model, using contrasts to obtain an estimate of the difference between the treatment and placebo at the Week 12 visit (Visit 5). Statistical significance of the Week 12 treatment difference will be tested. All SVC measurements from planned study visits prior to the Week 12 visit will be included in the estimation of the model.

SAS code in the following fashion will be used to perform the computations:

```
proc mixed data = ADEFF order = data alpha = 0.05 covtest;
  where ITTFL = "Y" and PARAMCD = "SVCPPSUP" and
    AVISIT in ("Week 2", "Week 4", "Week 8", "Week 12");
  class TRTP(ref = "PLACEBO") AVISIT STRATAR USUBJID SITEID;

  model CHG = BASE STRATAR TRTP AVISIT TRTP * AVISIT / ddfm = KR;
  repeated AVISIT / subject = USUBJID type = UN R;
  random SITEID / type = VC;

  estimate "Treatment Difference at Week 12"
    TRTP 1 -1 TRTP * AVISIT 0 0 0 1 0 0 0 -1 / cl;
run;
```

In the primary analysis, missing data are imputed using multiple imputation. As a result, the analysis above is repeated for each of the imputed data sets with the use of a by-statement. The analysis results are then pooled for inference according to the methods described in 6.2.5.

In additional analyses, data from all planned visits through 48 weeks will be included in the MMRM, and the treatment effect will be estimated with contrasts at each study visit. Further, a random slope model will be fitted, with visits' actual study days replacing the visit factor.

Changes in SVC (supine) between the last measurement while on treatment and the post-treatment measurement from their End of Study visit will be described.

Subgroup analyses will be conducted by removing the randomization stratum effect from the primary analysis model, and including the subgroup term and its interaction with treatment.

Descriptive statistics of SVC (supine) will also be presented by visit, treatment group, and angle of measurement position. The angle is categorised into three groups: 1) completely flat (0 degrees); 2) slightly elevated (up to 15 degrees); 3) unable to perform supine (> 15 degrees). The effect of angle of measurement will also be explored in an additional analysis, where the angle will be included as a factor in the primary analysis MMRM.

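### The angle-constancy population in SAP 7.5.4.6 and 7.5.4.8 lets angle changes after Week 12 decide who enters a Week 12 analysis

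*SAP*

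**What the plan says.** SAP 7.5.4.6 gives its method as "Use a new analysis population consisting only of subjects who had the same SVC supine measurement angle throughout their study visits". SAP 7.5.4.8 repeats the rule and also sets values taken above 15 degrees to missing. Both apply the population to the "Primary analysis SVC MMRM" and to all time-to-event endpoints with an SVC component. Neither gives a cut-off, and the heading of 7.5.4.6 refers to change during the study as a whole.

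The primary model stops at Week 12. SAP 7.5.1.1 says "All SVC measurements from planned study visits prior to the Week 12 visit will be included in the estimation of the model", and its code selects Weeks 2, 4, 8 and 12. SVC measurement continues after that. Protocol 6.2.1 says "SVC (supine) will be assessed once at each visit during the study including the baseline (visit 1"), and the visit list in SAP section 2 continues with "12 weeks (V5), 24 weeks (V6), 36 weeks (V7) and 48 weeks (V8").

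SAP 7.5.1.1 sorts angle into three categories: flat, raised by up to 15 degrees, and "3) unable to perform supine (> 15 degrees").

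For the per-protocol sets, SAP 6.1 reasons as follows: "would not be desirable to exclude subjects from the PP analyses due to important protocol deviations occurring only after the endpoint has already been assessed". It therefore creates PP1 (to Week 12) and PP2 (to Week 48).

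Two other planned analyses deal with angle and remove no subjects. SAP 7.5.4.7 sets values above 15 degrees to missing and imputes where applicable. SAP 7.5.1.1 adds angle as a factor to the primary MMRM.

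**The concern.** Membership of this population is settled by events after randomisation and, for the Week 12 model, partly by events after the endpoint has been measured. A subject with the same angle from baseline to Week 12 who is propped up at Week 36 loses all the Week 2 to 12 data. For a time-to-event endpoint, a subject whose event came at Week 4 can be removed, event included, because of an angle change months later.

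Retention also depends on length of follow-up. Subjects who stop treatment are followed for ALSFRS-R, ventilatory support and survival (Protocol 6.1.6), and COVID-19 telephone visits omit SVC (Protocol 6.6). Someone with fewer SVC visits has fewer chances to change angle and is more easily kept.

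The purpose of these analyses is to show whether inconsistent positioning explains the primary result. If the rule also selects on decline, a difference from the primary estimate could come from angle or from selection, and these two analyses alone could not tell them apart.

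**Working it through.** **1. Timing.** The Week 12 model uses four post-baseline visits (Weeks 2, 4, 8, 12). The rule can also be triggered at three later on-treatment visits (Weeks 24, 36, 48). The SAP does not say whether the screening and end-of-study SVC measurements count, or whether the same angle means the same category or the same degrees.

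**2. Anchor to the plan's own figure.** Inputs from SAP section 5: difference 3.6, SD 10, two-sided 5%, 90% power.

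n per group = 2 × (1.960 + 1.282)² × 10² / 3.6² = 162.1, so 163. The plan states 164; the noncentral t-test gives 90.2% power at 164 per group. The figure is reproduced.

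**3. If angle change is unrelated to decline.** Only precision is lost. Take 80% of 300 and 150, that is 240 and 120 evaluable. The noncentrality is 3.6 / (10 × √(1/240 + 1/120)) = 3.22, and power is 89.5%. If the rule removes a share from each group:

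| Removed | Power |
|---|---|
| 10% | 86% |
| 20% | 82% |
| 30% | 77% |
| 40% | 70% |

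The shares are assumptions; the documents give none.

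**4. If it is related: simple identity.** Let p be the share excluded in a group and e the extra Week 12 decline of excluded over retained subjects. The retained mean is the full mean plus p × e, so the treatment difference shifts by p(levosimendan) × e(levosimendan) − p(placebo) × e(placebo). Assume e is 5 to 8 points in both groups:

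- 10% levosimendan, 20% placebo: −0.5 to −0.8 points.
- Equal shares: 0.
- 20% levosimendan, 10% placebo: +0.5 to +0.8 points.

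**5. If it is related: simulation.** Taken from SAP section 5: 2:1 allocation and a placebo change of −8.5 at Week 12 (the BENEFIT-ALS row of the table). Assumed: linear decline, between-subject slope SD 0.6 per week, residual SD 6, complete follow-up, and a logistic chance of angle change at each visit with intercept −4 and log-odds rising by 0, 0.5 or 1 per 10 points of decline. The implied Week 12 SD is √((12 × 0.6)² + 6²) = 9.4, close to the planned 10. Estimates are differences in Week 12 means, without imputation. The drug effect is on slope, 0.3 per week.

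| Link | Excluded, placebo / levosimendan | Excluded only for a change after Week 12 | True | SAP rule | Changes to Week 12 only |
|---|---|---|---|---|---|
| None | 12% / 12% | 5% | 3.60 | 3.59 | 3.59 |
| Moderate (0.5) | 31% / 23% | 17% | 3.56 | 2.96 | 3.54 |
| Strong (1) | 57% / 41% | 35% | 3.60 | 1.96 | 3.49 |

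Other effect shapes:

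- Immediate step of 3.6: the SAP rule gives 3.42 (moderate) and 3.07 (strong).
- Benefit only after Week 12, true Week 12 difference about 0: −0.4 and −1.1.
- Harm only after Week 12, true Week 12 difference about 0: +0.6 and +1.4.
- No drug effect: the difference stays near 0, although retained placebo subjects decline by 6.5 or 3.2 instead of 8.5.

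In these runs, limiting the rule to changes up to Week 12 removes nearly all of the bias.

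**The case against.** The strongest reply is that nothing in the documents says why angles change. The only textual hint is the label on the top category. The rule also catches moves between flat and slightly raised, and moves to a flatter position; site practice could explain these equally well. This stands: the link to decline is an inference, and without it the cost is precision only.

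Three stronger readings are tempting, and the documents do not support them.

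- A reader might take angle change to be an established marker of orthopnoea. Protocol 1.2.1 says early respiratory signs often appear when lying down, which makes a link plausible but does not state it.
- A reader might conclude that the angle question cannot be answered. SAP 7.5.4.7 and the angle-adjusted MMRM address it without excluding anyone. Their cover is partial: 7.5.4.7 ignores shifts between flat and slightly raised, and the adjusted model conditions on a post-baseline covariate.
- A reader might take 0.5 to 0.8 points, or the simulated values, as the expected bias against levosimendan. They follow from assumed shares and assumed decline, and the sign reverses under other assumptions.

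It can also be said that PP1 concerns protocol deviations, which an angle change is not said to be, and that visits after Week 12 are relevant to endpoints running to Week 48. The first is fair, but the SAP's reasoning about timing carries over. The second does not justify using changes that follow a subject's event or censoring. If the sponsor meant only the visits in each model, the wording should say so.

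**Conclusion.** The point holds in a limited form. As written, an angle change after Week 12 removes a subject's Week 2 to 12 data from two sensitivity analyses of the Week 12 endpoint, contrary to the reasoning that the SAP applies to its per-protocol sets. If angle change is unrelated to decline, the loss is precision: power goes from 89.5% to between 86% and 70% for 10% to 40% removed. If it is related, the population is selected on post-randomisation outcome and the estimate can be biased, with size and direction depending on quantities that the documents do not give.

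The primary ITT result is unaffected, and these analyses are supportive. The point is minor, but worth correcting because the change is small.

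**What to change.** Reword SAP 7.5.4.6, and the matching step of 7.5.4.8, as follows.

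- Keep all ITT subjects. Set to missing only SVC values taken in an angle category (0, up to 15, above 15 degrees) different from that subject's baseline category, and impute as in the primary analysis. In 7.5.4.8, continue to set values above 15 degrees to missing as well.
- For the Week 12 MMRM, let no angle change after Week 12 determine who is included. If a subject-level exclusion is kept, count only changes from baseline to Week 12, as PP1 does for deviations, and label the analysis as conditioning on post-baseline data.
- For the time-to-event endpoints, apply the value-level rule to the SVC component only. Do not let angle changes after the event or censoring define the population.
- State that angle means category, and which visits count, including screening and end of study.

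The cost is SAP wording and more imputed values. The imputation assumes data missing at random. The model in SAP 6.2.5 uses SVC at other visits, treatment group, strata, sex, age group and riluzole use, but not angle, so the assumption may fail if angle change marks decline. The tipping-point analysis in 6.2.5, which the SAP only says will be considered, can probe this and could be committed to here.

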7.5.4.7 Exclude SVC supine measurements performed with > 15 degree angle

Method:

- Treat SVC data performed with > 15 degree angle as missing.
- Follow primary analysis methods otherwise: i.e. impute if applicable.

Analyses that will be adjusted:

- Primary analysis SVC MMRM.
- All analyses of time-to-event endpoints with SVC components.

7.5.4.8 Combined impact of position and angle on SVC supine results

Method:

- Use a new analysis population consisting only of subjects who had the same SVC supine measurement angle throughout their study visits.
- Treat SVC data performed with > 15 degree angle as missing.
- Follow primary analysis methods otherwise: i.e. impute if applicable.

Analyses that will be adjusted:

- Primary analysis SVC MMRM.
- All analyses of time-to-event endpoints with SVC components.

7.5.4.9 Adjust for riluzole use at baseline

Method:

- Include a term in the model for riluzole use at baseline.
- Assume no interaction effects.

Analyses that will be adjusted:

- Primary analysis SVC MMRM.
- Slope of change in the ALSFRS-R respiratory domain through 48 weeks

7.5.4.10 Adjust for effect of paper questionnaire collection

Method:

- Include term in model for whether data point was collected electronically or on paper.

Analyses that will be adjusted:

- MMRM analyses of: ALSFRS-R, CGI, Borg CR10, ESS, PSQI.
- Cox models of time-to-event endpoints with ALSFRS-R components.

7.5.4.11 Exclude efficacy data after initiation of NIV

Method:

- Treat data points collected on or after the date of NIV initiation as missing.
- Follow primary analysis methods otherwise: i.e. impute if applicable.

Analyses that will be adjusted:

- Primary analysis SVC MMRM
- CAFS through 48 weeks
- Time to respiratory event
- CGI through 48 weeks
- Supine Borg CR 10 scale at 12 weeks
- Slope of change in the ALSFRS-R respiratory domain through 48 weeks

7.6 Pharmacokinetics and pharmacodynamics

Concentration levels of levosimendan, OR-1855, OR-1896 and riluzole will be reported using descriptive statistics. Concentrations of levosimendan and its metabolites will also be reported by acetylation status.

Concentration-effect plots will be shown with respect to supine SVC and QTcF/QTcB.

Concentrations of levosimendan and its metabolites will be summarised with descriptive statistics at each visit by acetylation status (2 levels, with a third pooled group) and previous antibiotic use status. Previous antibiotic use will be categorised as ever-use, and additionally as 0, 1, 2, or 3+ uses. Antibiotic use status will be updated at each visit. Antibiotics will be identified among concomitant medications with the 2nd level ATC codes J01, J02, J04 and J05.

A more detailed population-level analysis of pharmacokinetics/pharmacodynamics will be planned and reported separately.

7.7 Pharmacogenomics

Acetylation status will be determined by bioanalytics, and categorized into four and two levels for reporting. Descriptive statistics for both will be reported by treatment group.

The two-level categorization of acetylation status will be used to stratify the reporting of concentration levels of levosimendan and its metabolites, dose changes, and safety. It will also be used to determine subgroups for the statistical analysis some efficacy endpoints (see 6.2.14).

7.8 Exploratory biomarkers

Analysis of exploratory biomarkers will be planned and reported separately.

The analysis is currently planned to at least describe correlations between change from baseline in ALSFRS-R and supine SVC, and change from baseline in creatinine, creatine kinase, troponin T, LDH, albumin, ALP, bilirubin, GGT, and glucose.

7.9 Safety

The analyses presented in this section will be reported for the Safety population, including all subjects having received any study treatment.

